The sample consisted of 36 women and 13 men, divided into two age groups: young people between 18 and 30 years old ($22,438 \pm 3,898$) and adults between 31 and 64 years old ($50,212 \pm 9,633$). In terms of origin, 23 were residents of Plasencia (Spain) and 26 in Castelo Branco (Portugal). The descriptive characteristics of the sample are detailed in Table 1.

Table 1. Descriptive characteristics of the sample.

VARIABLES	Total n=49	Origin	Young Men (mean±SD)	Adult Men (mean±SD)	Young Women (mean±SD)	Adult women (mean±SD)
AGE (years)	41,143± 15,485	Spain Portugal	20±2,828 26±NP	46,333±13.317 46,857±10,495	24,111±3,723 19±2	49±9,367 53.50±8.609
	70,545± 12,705	Spain Portugal	80±14,142 69±NP	87,333±17,926 80,714±11,572	68,667±13,684 66,750±8,995	64,411±7,193 66.857±11.016
HEIGHT (m)	1,664±0 ,085	Spain Portugal	1.82±0.113 1.7±NP	1.733±0.025 1.757±0.060	1,652±0.074 1.657±0.049	1.618±0.068 1,616±0.057
	25,404± 3,626	Spain Portugal	24,026±1,280 23,875±np	29,170±6,725 26,148±3,488	25,069±4,334 24,372±3,837	24,611±2,350 25,552±3,548

n: sample size; SD, standard deviation; NP: Not applicable; kg: kilogram; M: Metro; BMI, body mass index; m^2 : Square meter.

Randomization, masking, and experimental design

Participants were randomly assigned to distinct groups using free software Epidat 4.0 (2011, Galicia, Spain). The blinding was double-blind, so that neither the investigators nor the participants knew the group assigned to the participant until the completion of the study and statistical analysis.

The total number of participants was divided into three groups: a control group (T0) (n=12), in which no participants had a skin infection, and two different treatment groups (T1 and T2) (n=37), with diverse levels of EC. The rest of the participants were included in these two treatment groups, including both infected (n=32) and healthy (n=5) participants. Thus, group T1 (n=25) had 23 participants with infection and 2 healthy participants, and group T2 (n=12) had 9 participants with infection and 3 healthy participants.

The clinical evaluation of the participants was carried out before the start of treatment and, subsequently, on days 15, 30, 45 and 60 of treatment, except for cultures, both mycological and bacterial, which were performed at baseline, at 30 days and at 60 days of treatment. All reviews, sampling, and data collected were performed by the same observer.

Choice of EO, base cream, and preparation of treatments

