Scans and measurements were performed in a temperature-controlled room (20-24°C) and participants aired their bare feet for 10 minutes before starting the procedures, to normalize the temperature. In the first session they were weighed and measured (SECA 701, Vogel & Halke Hamburg, Germany), calculating the BMI(2). After normalizing the temperature, the physical examination was carried out, samples were taken, and data were obtained.

The Corneometer CM 825® (Electronic Courage-Khazaka, Cologne, Germany) with a measuring surface of 49 mm, a frequency of 0.9–1.2 MHz and an accuracy of $\pm 3\%$, was used to assess the superficial hydration of the skin (3). Five reference points were measured, both at the dorsal level and at the plantar level (Figure 2), obtaining three measurements from each point to later calculate the average hydration of each location analyzed.

[figure not shown]

Figure 2. Location of the 5 reference points on the feet for assessment of superficial hydration. (A) Dorsum of the foot: (1) dorso-distal point, above the central metatarsal heads. (B) Sole of the foot: (2) interdigital-plantar point, between 3rd and 4th digital space, (3) central point of the internal arch, (4) central point of the external arch, and (5) central point of the calcaneus.

Regarding the diagnosis of possible infections present in the feet, the following tests were performed:

- Wood's Light Examination

The feet of the participants were examined with a Wood L1004® lamp (Weelco, Barcelona, Spain) at maximum power (41) and at a distance of 10-15 cm from the surface to be examined. Long-wave ultraviolet radiation allows visual observation of the fluorescence emitted by *Pseudomonas aeruginosa*, *Microsporum audouinii*, *Microsporum canis*, *C. minutissimum*, *T. schoenleinii*,(4) among

others, whose color varies depending on the pathogen. The areas that fluoresced were recorded along with the color of the fluorescence in each review conducted from the beginning of the study to the day of its completion.

- Potassium hydroxide (KOH) test and mycological culture

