Statistical analysis was performed using the statistical analysis program IBM-SPSS Statistics for Windows version 25 (IBM Corp. Armonk, NY, USA). Some figures have been obtained using the Python programming language, using the Seaborn library (Waskom, M. L., (2021). Seaborn: statistical data visualization. *Journal of Open-Source Software*, 6(60), 3021, <https://doi.org/10.21105/joss.03021>).

Normality was assessed using the Shapiro-Wilk test. To evaluate the influence of different variables on infection remission, a Cox regression model was used, and survival curves of significant factors were plotted. To compare the efficacy of different EC concentrations, survival curves were compared using the Log-rank test. The Mann-Whitney U test was used to assess hydration averages according to sex. To check if there were improvements in hydration due to the use of the cream with different concentrations of EC (T1 and T2) compared to the control group (T0), hydration levels were compared using Kruskal-Wallis tests, using the Mann-Whitney U test with correction of p-values by the Bonferroni method for multiple comparisons.

In all statistical tests, significance was considered when p-value<0.05 and high significance when p-value<0.01.

2. Results

Analysis of the Elemental Composition of Commercial S. S.

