Variable	B (coef.)	Exp(B)	IC 95%		p-value
			Lim. Inf.	Lim. Sup	
Stature	-0.02	0.98	0.73	1.30	0.874
Weight	0.01	1.01	0.73	1.40	0.948
BMI	-0.04	0.96	0.39	2.40	0.938
Age	0.03	1.03	0.54	1.97	0.918
Sex	-0.64	0.52	0.20	1.35	0.181

Coef: coefficient; Exp: exponent; B: correlation coefficient; CI, confidence interval; Lim. Inf: lower bound; Lim. Sup: upper limit; *: statistically significant.

[figure not shown]
Regarding the possible relationship between anthropometric and sociodemographic variables and the efficacy of treatment for bacterial infections, it was observed that only sex showed a statistically significant relationship (p-value=0.028) (Table 9).

Table 9. Cox model for different anthropometric and sociodemographic variables and bacterial infection.

Variable	B (coef.)	Exp(B)	IC 95%		p-value
			Lim. Inf.	Lim. Sup	
Stature	0.11	1.12	0.82	1.54	0.484
Weight	-0.08	0.93	0.64	1.34	0.684
BMI	0.13	1.14	0.41	3.21	0.803
Age	0.55	1.74	0.82	3.67	0.146
Sex	1.41*	4.11	1.16	14.50	0.028*

Coef: coefficient; Exp: exponent; B: correlation coefficient; CI, confidence interval; Lim. Inf: lower bound; Lim. Sup: upper limit; *: statistically significant.

To assess the efficacy of the treatment over time according to sex, a cumulative survival curve was used (Figure 6) and the proportion of individuals in whom the resolution of the infection over time was observed was represented, observing that the healing time was shorter in women than in men and, therefore, a faster resolution of bacterial infection is observed in women.

**Figure 6.** Cumulative survival curve as a function of sex.

Finally, in relation to skin hydration, significant differences were obtained according to sex (p-value ≤ 0.010), with women having higher hydration averages (Table 10).

Table 10. Results of the Kruskal-Wallis tests for the analysis of hydration according to sex.

Landmarks per foot	Sex	Initial		15 days		30 days		45 days		60 days	
		Media±Sd	p-value								
Dorsal R	Woman	34.507±9.834	0.146	41.904±13.322	0.511	44.364±13.907	0.439	42.674±13.989	0.408	43.871±16.218	0.171
	Man	29.306±9.159		40.966±18.823		44.358±21.589		37.933±10.723		36.837±12.851	
Digital Plant R	Woman	29.453±11.772	0.115	39.738±16.234	0.075	37.465±14.911	0.044*	36.737±15.137	0.048*	45.303±18.070	0.015*
	Man	23.450±10.769		31.391±12.869		27.967±16.632		28.604±10.934		24.685±11.913	
Inner Arc R	Woman	28.401±19.944	0.221	32.539±22.396	0.541	31.884±20.830	0.318	29.654±18.746	0.318	30.272±18.633	0.480

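### The reported sex difference in skin hydration (p ≤ 0.010) misstates Table 10: 14 of 50 unadjusted p-values are below 0.05, two equal 0.010 and none is lower

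*Combined protocol and SAP*

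**What the plan says.** Under Variables and statistical analysis, the test for sex is named: "The Mann-Whitney U test was used to assess hydration averages according to sex". The decision rule is general: "In all statistical tests, significance was considered when p-value<0.05 and high significance when p-value<0.01". A multiplicity correction is named only for the treatment groups, where Kruskal-Wallis tests are followed by pairwise comparisons "using the Mann-Whitney U test with correction of p-values by the Bonferroni method for multiple comparisons".

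Hydration was measured on each foot: "Five reference points were measured, both at the dorsal level and at the plantar level". The clinical evaluations took place "before the start of treatment and, subsequently, on days 15, 30, 45 and 60 of treatment".

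The Results section then reports, citing Table 10, that "significant differences were obtained according to sex (p-value ≤ 0.010), with women having higher hydration averages". It names no site and no visit. The table's caption reads "Results of the Kruskal-Wallis tests for the analysis of hydration according to sex", and the table has no column of adjusted p-values.

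**The concern.** A reader of the Results sentence alone would conclude that women and men differ in hydration at a level of 0.010 or better, generally across the foot and throughout the study. Table 10 shows something much more mixed. Most comparisons are not significant by the plan's own rule, no site reaches 0.05 at day 15, and the quoted figure is the smallest p-value in the table, presented as if it were the largest.

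The 50 comparisons are also repeated looks at the same 49 people (two feet, five sites per foot, five visits). The nominal hits are therefore not independent confirmations, and with 50 looks some small p-values are expected even if there is no difference. What is at stake is a secondary conclusion stated with more certainty than the evidence gives. The infection results are not affected.

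**Working it through.** **Inputs.** Table 10: 10 sites × 5 visits = 50 p-values. Sample: 36 women and 13 men. Significance rule: p<0.05, high significance p<0.01, both strict.

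**1. Can the stated bound be reproduced?** Counts by visit:

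| Visit | p<0.05 | Smallest p |
|---|---|---|
| Initial | 3 of 10 | 0.012 |
| Day 15 | 0 of 10 | 0.075 |
| Day 30 | 3 of 10 | 0.010 |
| Day 45 | 3 of 10 | 0.038 |
| Day 60 | 5 of 10 | 0.010 |
| All | 14 of 50 | 0.010 |

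The largest value is 0.679, and 50 − 14 = 36 are not below 0.05. Three readings of the bound were tried:

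- All cells at or below 0.010: false, since only 2 of 50 are (right heel at day 30, left heel at day 60).
- All significant cells at or below 0.010: false, since the 14 run from 0.010 to 0.048 and 12 exceed 0.010.
- The smallest p-value is 0.010: true, but that is a lower bound, not an upper one.

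The 14 sit in five of the ten sites: right digital-plantar (3), right heel (3), left digital-plantar (2), left external arch (3) and left heel (3).

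**2. Stars and test name.** The right heel at the initial visit has p = 0.051 and carries one star, although 0.051 > 0.05. The two values of 0.010 carry two stars. An unrounded value from 0.0095 up to just under 0.010 would print as 0.010 and meet the rule, so these cannot be judged from the table. The caption says Kruskal-Wallis and the methods say Mann-Whitney; with two groups the two tests are nearly equivalent.

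**3. Multiplicity over 50 tests.**

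- Bonferroni threshold: 0.05 / 50 = 0.001. Smallest adjusted p: 50 × 0.010 = 0.50. Holm gives the same minimum. With 0.0095 in place of 0.010, 50 × 0.0095 = 0.475.
- Benjamini-Hochberg: the smallest of 50 × p(i) / i falls at ranks 4 and 5, where 50 × 0.012 / 4 = 0.15 and 50 × 0.015 / 5 = 0.15.
- Survivors at 0.05: none by any of the three.
- For scale, under independence and no true difference, 50 × 0.05 = 2.5 nominal hits are expected, and the chance of at least one is 1 − 0.95^50 = 0.923. The tests here are correlated, so these figures are only a guide.

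**4. Does the choice of family matter?** Yes. Day 60 alone has p = 0.010, 0.012, 0.015, 0.019, 0.048, … At rank 4 the Benjamini-Hochberg limit is 4 × 0.05 / 10 = 0.020, and 0.019 is below it, so four are kept. Bonferroni and Holm within each visit keep none. Bonferroni within one heel over five visits gives 5 × 0.010 = 0.050. The documents define no family.

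**5. Direction and baseline.** The mean is higher in women in all 50 cells. At baseline the gap runs from 25.227 − 21.662 = 3.6 (left inner arch) to 27.532 − 18.307 = 9.2 (left digital-plantar). At day 60 it runs from 6.2 to 9.8 in nine sites. The tenth, right digital-plantar, shows 45.303 − 24.685 = 20.6, against 29.453 − 23.450 = 6.0 at baseline.

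**6. The anomalous cell.** For right digital-plantar at day 60, a Welch statistic from the printed summaries is 20.618 / √(18.070²/36 + 11.913²/13) = 20.618 / 4.47 = 4.61, p about 0.0001, against a reported 0.015. A rank test may differ from a t-test, so this is not proof of an error.

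Table 11 offers a second check. For this site the overall means implied by Tables 10 and 11 agree at the first four visits; at baseline, for example, (36 × 29.453 + 13 × 23.450)/49 = 27.86 and (12 × 29.630 + 25 × 26.538 + 12 × 28.846)/49 = 27.86. At day 60 the Table 10 total is 36 × 45.303 + 13 × 24.685 = 1951.8. With T0 at 36.998 and T2 at 27.466, T1 would have to average (1951.8 − 12 × 36.998 − 12 × 27.466)/25 = 47.1, up from 32.126 at day 45. The T1 value for that cell cannot be read in the text available here.

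**The case against.** The other side has several sound points.

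- **The plan does not favour sex over treatment.** Its Bonferroni step covers only the three pairwise group contrasts within one site and visit; Table 12 shows a factor of 3 (0.092 becomes 0.276). The group tests in Table 11 are not described as corrected across sites and visits either. With two sexes there is one contrast, so the plan's own rule would change nothing. The gap is general, not a double standard.
- **The tests are correlated.** Bonferroni and Holm over 50 are then conservative, and the count of survivors depends on a family the documents do not define.
- **The bound may be a slip of sign.** For Table 7 the document writes the smallest p-value with a ≥ sign (0.103). Written that way, ≥ 0.010 would be true of Table 10. Intent cannot be established, but the printed sentence still needs correcting.
- **No claim about response to the cream is made.** The sentence reports a difference by sex and does not attribute it to treatment. A reader might infer one; the text does not say so.

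A reader might also go further and conclude that the sex difference is refuted. The documents do not support that. The direction is the same in all 50 cells, the gap is there before treatment, and 14 nominal results is well above 2.5, although correlation prevents reading that excess as a formal test.

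What stands after all this is the wrong bound, the unqualified statement of significance, the star on 0.051, the mismatch in test name and the undescribed multiplicity.

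**Conclusion.** The point holds in a limited form. As printed, p ≤ 0.010 is wrong for 48 of 50 cells, and for 12 of the 14 that are nominally significant. A general statement of significance is not supported when 36 of 50 comparisons are not below 0.05 and none survives correction over 50. The direction, women higher, is fully supported by the table.

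The assumptions are these. The p-values are taken to be unadjusted, which is inferred from the methods text and the missing adjusted column, not stated. The statement that none survives applies to the family of 50; smaller families picked afterwards can keep some. The rank tests cannot be recomputed without individual data, and the Welch check assumes all 36 women and 13 men were measured at day 60. The importance is moderate: a reported conclusion changes in strength, but it is a side comparison.

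**What to change.** Text and table edits:

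1. Replace the sentence with wording such as: *women had higher means in all 50 comparisons; p-values ranged from 0.010 to 0.679, 14 of 50 were nominally below 0.05 and none was after correction over 50; these comparisons are exploratory.*
2. Remove the star on 0.051. Check the unrounded values of the two 0.010 cells before keeping their double stars.
3. Name the same test in the methods and in the Table 10 caption.
4. Check right digital-plantar at day 60 (45.303 against 24.685, p = 0.015) against source data, and compare the T1 mean in Table 11 with the 47.1 implied above.

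If one overall test of sex is wanted, fit a single repeated-measures model to the existing data: participant as random effect, with sex, visit, site, foot, group and sex-by-visit as fixed effects. Keep baseline as one of the outcome visits and do not also use it as a covariate. Several SDs are close to their means (for example 16.168 ± 11.812), so check the residuals or transform for skew.

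The cost is one model and a few edits, with no new data. The downside is that a result claimed as significant becomes a weaker, exploratory one.

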Of the participants who developed skin infections, 23 were women and 9 were men. The prevalence of skin infections by sex is shown in Table 3.

Table 3. Prevalence of infections as a function of sex.

Sex	Infections			Total
	Fungal	Bacterial	Mixed	
Women	3 (9.3%)	13 (40.6%)	7 (21.8%)	23 (71.7%)
Men	1 (3.1%)	6 (18.8%)	2 (6.4%)	9 (28.3%)
Total	4 (12.4%)	19 (59.4%)	9 (28.2%)	32 (100%)

%: Percentage.

The colorations observed with Wood's light in the interdigital spaces were coral red and opaque blue (Figure 3). The coral-red coloration corresponds to a superficial bacterial infection of the skin caused by *C. minutissimum*, known as erythrasma, and the dull blue coloration corresponds to a fungal infection caused by the dermatophyte *Trichophyton schoenleinii*.

[figure not shown]

Figure 3. Fluorescence of different color emitted by pathogens under Wood's light in interdigital spaces of the feet. (A and B) erythrasma with coral-red coloration (*) and (B) suspected *Trichophyton schoenleinii* with bluish coloration (↑).

Mycological cultures were used to determine the causative agents of fungal infections. The dermatophytes and yeasts that were identified were: *Trichophyton schoenleinii*, *Trichophyton verrucosum*, *Trichophyton tonsurans* and *Candida albicans*. On the other hand, the following bacteria were identified in bacterial cultures: *Corinebacterium minutissimum*, *staphylococcus haemolyticus*, *staphylococcus epidermidis*, *staphylococcus lugdunensis*, *micrococcus luteus* and *micrococcus sp.*

Efficacy of treatments

To test whether the EC-enriched cream was effective against fungal infections, the cumulative survival curves of the two treatments, T1 and T2, were plotted (Figure 4). 100% of fungal infections resolved within 30 days with both treatments, although the EC curve at 1% was higher than 0.5%.

[figure not shown]

Figure 4. Cumulative survival curves as a function of the two treatments for fungal infections.

In fact, the mean time to achieve remission in the T1 group (1%) was 11.61 days, compared to 14.00 days in the T2 group (Table 4). However, according to the Log-rank test, the differences between the two groups were not statistically significant (p -value=0.611). Therefore, both concentrations have similar efficacy in terms of the time required to achieve remission of infection.

Table 4. Mean and median survival time (in days) of remission of fungal infection for the two EC concentrations.

Group	Media				Median			

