Although descriptively variations in skin hydration are observed depending on the treatment applied, only the area of the "Outer Arch" of the right p-ie showed significant differences between groups, both at one and a half months of treatment ($p\text{-value}=0.028$) where the T1 group presented a lower hydration, and at its completion ($p\text{-value}=0.002$), with the T2 group having the lowest hydration (Table 1-1). After the pairwise comparison, statistically significant differences were obtained between the T0 and T1 groups at one and a half months ($p\text{-value}=0.016$), observing that the control group had greater hydration, and between the T0 and T1 groups ($p\text{-value}=0.021$) and the T0 and T2 groups ($p\text{-value}=0.003$) at the end of treatment where, as in the month and a half, the control group had greater hydration (Table 1-2).

Table 11. Results of the Kruskal-Wallis tests for the analysis of hydration as a function of time and treatment applied.

Landmarks per foot	G	Clinical Evaluation							
		Initial		15 days		30 days		45 days	
		Media±Sd	p-value	Media±Sd	p-value	Media±Sd	p-value	Media±Sd	p-value
Dorsal R	G. T0	35,506±9,364		46,356±17,565		47,787±18,500		41,144±12,744	47,612±19,149
	G. T1	32,481±9,077	0.600	39,537±14,093	0.405	42,690±16,888	0.669	40,626±13,840	0.775
	G. T2	32,095±12,123		41,366±13,255		43,522±11,821		43,332±13,482	41,433±17,052
Digital Plant R	G. T0	29,630±8,215		38,992±17,156		44,454±18,161		38,044±17,682	36,998±18,832
	G. T1	26,538±13,104	0.592	37,230±17,615	0.943	32,939±14,430	0.059	32,126±14,095	0.474
	G. T2	28,846±12,171		36,666±10,250		29,616±12,832		36,225±11,886	27,466±13,514
Inner Arc R	G. T0	31,117±15,186		31,721±18,640		35,890±23,178		32,205±18,994	37,761±17,694
	G. T1	28,705±22,666	0.135	33,491±24,892	0.687	29,179±18,094	0.457	28,441±20,519	0.633
	G. T2	17,731±9,006		25,278±12,703		25,831±17,795		24,487±9,525	21,633±11,244
External Arc R	G. T0	20,622±9,449		24,434±14,194		27,500±13,395		29,243±12,342	27,668±9,032
	G. T1	19,081±10,643	0.336	24,125±15,356	0.701	24,190±14,910	0.317	18,564±12,384	0.028*
	G. T2	15,119±8,104		20,323±14,354		19,487±11,907		20,989±11,010	13,874±7,691
Heel R	G. T0	14,873±9,495		19,435±13,382		28,527±20,929		21,406±16,765	17,062±7,272
	G. T1	14,966±14,056	0.654	21,629±19,017	0.778	19,897±13,953	0.212	17,934±15,610	0.898
	G. T2	11,102±5,294		15,928±10,798		16,457±12,132		15,501±6,685	11,152±6,825

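### Arm comparisons of hydration leave out sex, which is related to hydration at baseline and not reported by arm; at the right outer arch only the day-60 T0 v T1 result is realistically sensitive to this.

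*Combined protocol and SAP*

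**What the plan says.** Under *Variables and statistical analysis*, the sexes are compared on hydration by Mann-Whitney tests. For the arms, "hydration levels were compared using Kruskal-Wallis tests", followed by pairwise Mann-Whitney tests with Bonferroni correction. Neither comparison includes the other factor. Sex does enter the Cox models for infection (Tables 8 and 9).

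In *Results*, Table 10 is summarised as showing significant sex differences, "with women having higher hydration averages (Table 10"). Tables 11 and 12 then report the arms. Only the right outer arch differs, at days 45 and 60: "statistically significant differences were obtained between the T0 and T1 groups at one and a half months", and T0 differs from both oil arms at day 60. In each case the control cream has the higher hydration.

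On composition: "The sample consisted of 36 women and 13 men". The arms are "a control group (T0) (n=12), in which no participants had a skin infection"; "group T1 (n=25) had 23 participants with infection and 2 healthy participants"; and "group T2 (n=12) had 9 participants with infection and 3 healthy participants". Table 1 splits the sample by origin, age group and sex, not by arm. No stratification by sex is described.

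**The concern.** Sex is related to hydration before any cream is used, so a difference between arms in the share of men carries over into the hydration gap between them. With 13 men spread over arms of 12, 25 and 12, a difference of a few men is easy to get by chance, and the reader cannot check it. T0 is also drawn only from uninfected participants, few of whom are men. At stake is whether the declared differences between the control cream and the oil arms partly reflect who was in each arm. The sex comparison in Table 10 pools the arms at days 15 to 60 and is exposed in the same way.

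**Working it through.** **Inputs.** Sex means come from Table 10, arm means from Table 11 and p-values from Table 12. Arm sizes and infection counts come from *Randomization, masking, and experimental design*; sex by infection status comes from the microbiological results. The T1 day-60 column is not legible in the text available, so that mean is back-calculated.

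**1. Reproducing a printed figure.** Right outer arch, day 60, T0 v T2, with a t test standing in for the rank test:
- t = (27.668 − 13.874) / √((9.032² + 7.691²)/12) = 13.794/3.42 = 4.03, p = 0.0006, times 3 = 0.0017.
- Table 12 gives 0.001 and 0.002, so this agrees. For day-45 T0 v T1 the stand-in is looser (0.019 against 0.008).

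**2. Is sex related to hydration before treatment?** Baseline women minus men, in Table 10 order: 5.20, 6.00, 6.76, 4.42, 6.25, 5.58, 9.23, 3.57, 6.62, 7.40. All are positive; the mean is 6.1.

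**3. What the counts imply for T0.** "Of the participants who developed skin infections, 23 were women and 9 were men". The 17 uninfected are therefore 36 − 23 = 13 women and 13 − 9 = 4 men.
- T0 holds 0 to 4 men of 12.
- T1 holds at most 9 infected plus 2 healthy men, 11/25. So T1's share of men can exceed T0's by at most 0.44.
- For T2 against T0 the limit is 1.0.

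**4. Size of bias.** Bias = (difference in share of men) × (women − men gap). At the right outer arch:

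| Comparison | Arm gap | Sex gap | Difference in share | Bias |
|---|---|---|---|---|
| Day 45, T0 v T1 | 29.243 − 18.564 = 10.68 | 22.125 − 21.646 = 0.48 | 0.44 (limit) | 0.21 (2%) |
| Day 60, T0 v T2 | 13.79 | 22.006 − 15.783 = 6.22 | 0.25 | 1.6 (11%) |
| Day 60, T0 v T2 | 13.79 | 6.22 | 0.50 | 3.1 (23%) |
| Day 60, T0 v T2 | 13.79 | 6.22 | 1.00 (limit) | 6.2 (45%) |

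Subtracting the bias from the T0 v T2 gap and repeating the t test gives p × 3 of about 0.005, 0.015 and 0.11 for the last three rows. Only near-complete imbalance takes it past 0.05.

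**5. Day 60, T0 v T1.**
- Overall mean = (36 × 22.006 + 13 × 15.783)/49 = 20.355.
- T1 mean = (49 × 20.355 − 12 × 27.668 − 12 × 13.874)/25 = 19.96. Gap = 27.67 − 19.96 = 7.71.
- Raw p = 0.008 corresponds to z = 2.65. The Bonferroni cut-off (0.05/3, two-sided) is z = 2.39. A fall of 1 − 2.39/2.65, about 9.7%, removes significance.
- 0.097 × 7.71 = 0.75 units; 0.75/6.22 = 0.12, so about 12 points in the share of men. Allowing for the smaller residual variance (sex explains 6%) raises this to about 15.
- The results text prints 0.021 where Table 12 has 0.024. Using 0.021 (raw 0.007, z = 2.70) gives about 14 points.

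**6. How likely is that?** Assume sex is random within infection status. Men in T0 are then hypergeometric (4 men among 17, 12 drawn). The remaining uninfected men split over 2 places in T1 and 3 in T2. Infected men in T2 are hypergeometric (9 among 32, 9 drawn), with the rest in T1. T1's share of men minus T0's has mean 0.04 and SD 0.096. It is at least 12 points in about 18% of allocations, at least 16 points in about 9%, and at least 25 points in about 1.6%. For T2 against T0, the difference in women's share has a 95% range of −0.25 to +0.33.

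**The case against.** If allocation was random, unadjusted rank tests are valid and their p-values already allow for chance imbalance, so adjusting for sex mainly buys precision. That argument is sound, but it needs arms drawn from one population, and T0 contains only uninfected participants.

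Second, sex is not significant at the right outer arch at any visit (p = 0.180, 0.679, 0.147, 0.626, 0.087), and most of the 50 comparisons in Table 10 are above 0.05. This stands as a limit on the size of the effect. It does not undo the consistent baseline direction.

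Third, the one sensitive result rests on a reconstructed mean and a normal approximation. The Table 10 gap may itself contain arm effects: if T0 had proportionately more women, the higher T0 readings would inflate the 6.2, and the imbalance needed would exceed 12 points. This also stands, so the figure is a rough guide.

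A reader might infer that, because the day-60 sex gap averages 7.1 and the T0 − T2 gap averages 7.6 over nine landmarks (leaving out right digital-plantar, where the women's mean does not fit its p-value), sex could account for the arm differences. The documents do not support that. Bias is the sex gap multiplied by the difference in share, not the gap itself. At the only landmark with declared differences the ratios are 6.2 to 13.8 and 0.48 to 10.7. Nor can sex have produced an apparent hydration benefit of the oil, since the reported direction is lower hydration in the oil arms.

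**Conclusion.** The omission is real and cheap to repair, and its reach is narrow. Sex is related to hydration at baseline, is left out of the arm comparison, and cannot be checked by arm.

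- **Day 45, T0 v T1 (adjusted p 0.023):** not explained by sex. The sex and arm tables disagree slightly on the overall mean in this cell (by 0.22). If the men's mean is the misprint, the sex gap is about 1.3 and the bias at the 0.44 limit is about 0.6, or 5%, still below the 9.7% needed.
- **Day 60, T0 v T2 (adjusted p 0.002):** unlikely to be lost; a 50-point imbalance leaves about 0.015.
- **Day 60, T0 v T1 (adjusted p 0.024):** could lose significance if T1's share of men exceeded T0's by roughly 12 points. This happens in about 18% of allocations when sex is random within infection status.

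The actual split is unknown, so neither the size nor the sign of the bias is established; an imbalance the other way would widen the gap. Infection status (0/12, 23/25 and 9/12 infected in T0, T1 and T2) is the stronger confounder of any comparison with T0, and adjusting for sex leaves it in place.

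**What to change.** 1. Print the number of women and men in each arm.
2. Compare T0 v T1 and T0 v T2 on hydration with a rank-based ANCOVA containing arm, sex and the baseline hydration of the same landmark, keeping the Bonferroni correction.
3. Include arm in the sex comparison of Table 10 for days 15 to 60.
4. State that confounding by infection status limits every comparison with T0.

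All variables are already collected, so the cost is a re-run and two model degrees of freedom. Before using baseline as a covariate, check the left outer arch: its printed baseline values for T1 and T2 repeat those of the left inner arch. Also reconcile the adjusted p-values in the text (0.016, 0.021, 0.003) with Table 12 (0.023, 0.024, 0.002).
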